### 11.3 Safety Stopping Rule

An independent DSMB will be installed to periodically review accruing safety information, and if necessary, to determine whether study or individual subject stopping rules have been met.

The DSMB will periodically review the listing and summary tabulations of SAEs, deaths, solicited AEs, unsolicited AEs and AEs leading to withdrawal from further vaccination. After about 50% of subjects of treatment groups A, B, C and D completed Visit 3 (day 56), the DSMB will review safety and immunogenicity in order to evaluate the risk-benefit of the MV-CHIK administration and make recommendations to the sponsor regarding the further study conduct and/or protocol modifications, if needed. A written DSMB charter will be developed.

### **Individual subjects**

The following subjects will be discontinued from further vaccination:

- a. Subjects who develop a severe or life-threatening (grade 3 or 4) suspected adverse reaction (SAR) or laboratory abnormality.
- b. Subjects who develop a grade 3 solicited systemic adverse event that occurs without alternative etiology in the 7 days following the study vaccination.
- c. Subjects who develop a medical condition for which continued participation, in the opinion of the site principal investigator or appropriate sub-investigator, would pose a risk to the subject or would be likely to confound interpretation of the results.
- d. Pregnant subjects.

In case a subject has to discontinue the clinical study prematurely for any reason, he or she should be asked to perform an early termination visit. Additionally, women of childbearing potential will be followed up by a phone call, 3 months after the last vaccination to ensure no pregnancy occurred within this period as confirmed by a urine pregnancy test provided by the investigator.

### **Treatment group stopping rules**

If four or more subjects in a treatment group experience a treatment related grade 3 suspected adverse reaction (SAR) or laboratory abnormality, or one or more subjects in a treatment group experience a treatment related grade 4 SAR or laboratory abnormality, the study will be suspended pending an unblinded safety review of those subjects by the DSMB. This safety review might lead to the recommendation to discontinue a treatment group.

In case a treatment group has to discontinue the clinical study prematurely for any reason, the concerned subjects should be asked to perform an early termination visit. Additionally, women of childbearing potential will be followed up by a phone call, 3 months after the last vaccination to ensure no pregnancy occurred within this period as confirmed by a urine pregnancy test provided by the investigator.

**Entire study stopping rules**

The study will be stopped (no new enrollments and no additional vaccine administered) pending a full DSMB safety review if any of the following occurs:

- a. One or more subjects experience a suspected adverse reaction (SAR) that is both serious and unexpected, based on the reference safety information (Investigator's Brochure).
- b. One or more subject's death assessed by the investigator, medical monitor or sponsor as related to investigational product.
- c. One or more subjects develop laryngospasm, bronchospasm or anaphylaxis within 24 hours of vaccine administration.
- d. One or more subjects develop injection-site ulceration, abscess or necrosis.
- e. Two or more subjects experience generalized urticaria within 72 hours after administration of study product.

Upon completion of this review and receipt of the advice of the DSMB, the sponsor will determine if study entry or study dosing should be discontinued (or if a dose level should be dropped) or if study entry and study dosing may continue according to the protocol. The competent authorities and ethical committees will be informed whenever the study is stopped for DSMB review.

In case the entire clinical study has to discontinue prematurely or a dose level has to be dropped for any reason, the concerned subjects should be asked to perform an early termination visit. Additionally, women of childbearing potential will be followed up by a phone call, 3 months after the last vaccination to ensure no pregnancy occurred within this period as confirmed by a urine pregnancy test provided by the investigator.

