All subjects of the measles booster group M1 and M2 will receive five i.m. injections on study day -28, 0, 28, 168 and 196. The first vaccination will be Priorix® (or equivalent measles vaccine) on study day -28. Group M1 will receive MV-CHIK high dose vaccinations on day 0 and day 28 and placebo on day 168 and 196. Group M2 will receive placebo on day 0 and 28 and MV-CHIK high dose on day 168 and on day 196.

All subjects will be followed for safety and immunogenicity evaluation until day 224.

The estimated study duration per subject will be 33-37 weeks (~8 months), respectively. Overall study duration estimates to be 3 years from study initiation until reporting.

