#### **7.4 Premature discontinuation**

Subjects have the right to withdraw consent to participation in the clinical study at any time for any reason without naming it.

It will be documented whether or not each subject completed the clinical trial. If, for a subject, trial treatment or observations have been discontinued, the reason will be recorded. Volunteers have to be withdrawn for the following reasons:

- voluntary subject withdrawal for any reason
- at the discretion of the investigator
- if an adverse event (including a concomitant illness) develops, which is considered by the investigator incompatible with the continuation of the study
- if the administration of a drug, which is not permitted by the exclusion criteria, is necessary
- subject failure to comply with the requirements of the protocol
- violation of exclusion criteria 1, 7, 8, 10, 19, 20, 21, 22 and 23 during the study

For any subject discontinuing the study before schedule, the investigator will:

- ask the subject to take part, as far as possible, in the early termination visit in order to examine the subject's health conditions and perform the required blood sampling for the clinical blood tests.
- complete the eCRF, indicating in the final visit, the date of termination, the date and time of the last dose administration and the reason for discontinuing the study
- arrange for alternative medical care for the withdrawn subject, if necessary.
- record in the eCRF any follow-up if the subject was withdrawn due to an AE.

All subjects who are discontinued prior to Visit 0 will be replaced.

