### **8.2.9 Early Termination Visit**

Subjects, who are withdrawn or terminated the study prematurely for any reason, will undergo the following investigations if possible: blood sampling for immunogenicity 1, measles antibody titer, clinical chemistry, hematology, blood coagulation and all study sites except the two sites in Vienna serum sampling for cross neutralization and passive transfer analyses (immunogenicity 2). A urine sample will be obtained for urinalysis and pregnancy test in women of childbearing potential, symptom-directed physical exam, system-based assessment (only if

necessary according to symptom-directed physical exam) and evaluation of vital signs, body temperature and local tolerability (of previous vaccination site) will take place. The subjects will be asked if they experience arthralgia. Adverse events and concomitant medication will be recorded, if applicable. Subject diaries will be collected and checked for completeness. A urine pregnancy test kit will be provided to all women of childbearing potential, to be used 3 months after the last vaccination, and a follow up call will be performed by the site to enquire the test result.

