## **11.2 Post vaccination reactogenicity assessments**

Please also refer to Table 2 and section 8.2 for exact time points.

All subjects enrolled in the study and who receive at least one immunization (Priorix® or MV-CHIK) will be followed up for at least 28 days after the last immunization.

Adverse event rates will be used to evaluate the secondary study objective.

Serious adverse events: see below for detailed clarification

Medically attended adverse events: All adverse events, for which the subjects were seeking medical care (i.e. doctor's office, emergency service, hospital, but not use of self-medication).

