## 14.7 Reporting of Pregnancies

Women must not become pregnant during the entire clinical study period and 6 months after the last vaccination. If a subject becomes pregnant within this period, she must immediately inform the investigator of the pregnancy. The investigator will complete a corresponding Pregnancy Report Form and send the form within 24 hours after becoming aware to Assign Safety Desk via fax. The first notification can be done via phone (24-hours safety [contact]), nevertheless a written Pregnancy Report Form must be submitted for confirmation. If the pregnancy occurs during the study the subject should attend follow-up visits as planned. In addition, subjects who become pregnant during the study (and who received at least one dose) or subjects who become pregnant within 6 months after the last vaccination

(even in case of withdrawal or early termination for any reason) will be followed until pregnancy outcome, even if this occurs after the study is completed.

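### Dropping a dose level sends its subjects to an early termination visit, which the protocol does not reconcile with follow-up of all subjects to Day 224

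*Protocol*

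**What the plan says.** Protocol 11.3 has three levels of stopping rule.

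- **Entire study.** After its safety review the sponsor may stop study entry or dosing, or drop a dose level. The closing paragraph then says that if the whole study ends early or "a dose level has to be dropped for any reason, the concerned subjects should be asked to perform an early termination visit".
- **Treatment group.** "In case a treatment group has to discontinue the clinical study prematurely for any reason, the concerned subjects should be asked" to attend the same visit.
- **Individual subjects.** Listed subjects are taken off further vaccination. The early termination visit applies only if a subject has to leave the study.

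Section 8.2.9 says whom that visit is for: "Subjects, who are withdrawn or terminated the study prematurely for any reason, will undergo the following investigations if possible". SAP 2.9 records early termination on the study end page of the eCRF.

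The general follow-up statements are wider. Section 6.1: "All subjects will be followed for safety and immunogenicity evaluation until day 224". Section 11.2 says that everyone who receives at least one immunization "will be followed up for at least 28 days after the last immunization". Sections 13.2 and 14.5 run adverse event recording to Visit 6 (Day 224).

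On pregnancy, 7.4 lists among the reasons for mandatory withdrawal "violation of exclusion criteria 1, 7, 8, 10, 19, 20, 21, 22 and 23 during the study", and criterion 23 in 7.3 is pregnancy. Section 11.3, individual rule d, only stops further vaccination. Section 14.7 says: "If the pregnancy occurs during the study the subject should attend follow-up visits as planned".

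**The concern.** Stopping injections and ending participation are different decisions. For a dropped dose level, 11.3 moves from the first to the second without saying so. Followed as written, the arm that raised the safety question would lose its remaining scheduled visits, and with them the planned look for new events, the Day 56 and Day 224 safety laboratory tests and the later antibody samples. The other arms would keep theirs. The missing data would then depend on dose and on toxicity, in a trial that has the choice of dose and schedule as a secondary objective.

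The primary endpoint is also touched. SAP 2.7.1 analyses Day 56 titres, SAP 2.11 does not impute them, and SAP 6.2.1 and 6.2.2 list the early termination sample as a visit of its own. No rule maps that sample to Day 56, so a subject who leaves before Visit 3 contributes nothing to the primary comparison.

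**Working it through.** **1. The sections side by side**

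| Section | Who | Follow-up stated |
|---|---|---|
| 6.1 | all subjects | safety and immunogenicity to Day 224 |
| 13.2, 14.5 | all subjects | adverse events to Visit 6 |
| 11.2 | anyone immunized | at least 28 days after the last immunization |
| 14.6 | subjects with known events | serious events to an outcome; severe or related non-serious events to 28 days after administration |
| 11.3, dropped dose level | the subjects concerned | early termination visit, plus a pregnancy call at 3 months for women of childbearing potential |
| 8.2.9 | subjects who leave early | one visit, if possible, with no timing relative to the last dose |

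The fifth row cannot be squared with the first two unless the early termination visit is not an exit, and 8.2.9 and SAP 2.9 treat it as one. It clashes with the third row only if the visit falls less than 28 days after the last dose. It does not cancel the fourth row.

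**2. Scheduled follow-up that could be cut (maxima)**

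- Exit just after the Day 0 injection: 224 − 0 = 224 days.
- Exit just after the Day 28 injection: 224 − 28 = 196 days.
- Exit just after Visit 3: 224 − 56 = 168 days; the Day 56 titre is kept, while Days 196 and 224 are lost.

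**3. Day 56 titres and power**

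Inputs from protocol 13.4:
- Between doses: GMT 45.7 vs 22.4, log10 SD 0.6 in both groups, 60 per group, two-sided alpha 5%, equal-variance t-test, stated power 80%.
- MV-CHIK vs control: GMT 15.4 vs 7.3, log10 SD 0.6 vs 0.26, 60 vs 10, unequal-variance t-test, stated power 80%.

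The plan's own figures, from the noncentral t distribution:
- Dose comparison: d = log10(45.7/22.4) = 0.310. SE = 0.6 × √(1/60 + 1/60) = 0.1095. Noncentrality = 0.310/0.1095 = 2.83 on 118 df, so power is **80.1%**.
- Against control: d = log10(15.4/7.3) = 0.324. SE = √(0.6²/60 + 0.26²/10) = 0.1130. Noncentrality = 2.87 on 28.6 df, so power is **79.2%**.

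Both agree with the stated 80%.

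Now let one arm keep n Day 56 titres, with the comparator unchanged at 60 (or 10 controls):

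| n | dose comparison | vs 10 controls |
|---|---|---|
| 60 | 80.1% | 79.2% |
| 45 | 73.7% | 73.6% |
| 30 | 62.7% | 63.4% |
| 20 | 50.6% | 51.1% |

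For n = 30 in the dose comparison: SE = 0.6 × √(1/30 + 1/60) = 0.1342, noncentrality 2.31 on 88 df. The value 30 is an assumption, namely that the dose is dropped at the planned DSMB review, when about 50% of groups A–D have passed Visit 3, and that every remaining subject of that arm is enrolled and exits.

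**4. What a retained Day 56 sample would measure**

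- Stopped before Day 28: groups A and C have had one of two doses; B and D have had placebo only. The titre would not reflect the assigned regimen.
- Stopped between Day 28 and Day 56: the injections due before Day 56 have been given, so the titre does reflect it.

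Only the second set is a recoverable loss for the primary analysis.

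**5. Pregnancy**

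Three sections give three statuses for the same event: withdrawn (7.4 with criterion 23), off vaccination (11.3 d), and attending planned visits (14.7).

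**The case against.** The clause is a contingency, and several stronger inferences that a reader might draw fail.

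- *Safety follow-up ends altogether.* It does not. Section 14.6 keeps known serious events, and severe or related ones, under follow-up during and after participation, and the pregnancy call remains.
- *The 28-day minimum is broken.* Only if the visit is held sooner. No timing is set, and subjects are asked rather than obliged to attend.
- *The protocol confuses the two decisions throughout.* It does not. The individual rules in 11.3 separate them, and the group rule is conditional on the group having to leave the study. Only the dropped-dose clause joins them directly.
- *The loss falls exactly on the exposed.* B and D have had only placebo before Day 28, M2 has no MV-CHIK before Day 168, and each of A–D includes 10 control-vaccine subjects. Whom the clause covers is not defined. The SAP adds to this by giving M1 and M2 the low dose in Austria and the high dose in Germany, where this protocol gives the high dose.
- *Half of the 120 high-dose subjects in C and D, about 60, would lose Day 56.* The 50% refers to A–D together, and the other half may include people not yet enrolled, whose missing titres would not be caused by this wording.
- *The Phase 3 choice would be biased.* A dose dropped for safety is unlikely to go forward, so missing titres in that arm would seldom decide it.

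It is also fair that the DSMB may recommend protocol changes under a charter not seen here, and that the SAP of May 2018 still analyses all groups to Day 224. On pregnancy, 14.7 is the more specific text and 20.1 allows sponsor-approved exceptions to withdrawal.

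All of this narrows the point. None of it reconciles the dropped-dose clause with 6.1, 13.2 and 14.5.

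**Conclusion.** The point holds in a limited form. The dropped-dose clause, and the group rule when it applies, direct subjects to a visit that marks the end of participation, against stated follow-up of all subjects to Day 224 and event recording to Visit 6. The conflict with 11.2 depends on timing. Scheduled detection of new events, safety laboratory tests and immunogenicity samples would be cut short, by at most 224 days, mainly in the arm under suspicion.

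The fall from about 80% to about 63% power is an upper-bound illustration. It assumes that 30 of 60 titres in one arm are lost through this wording, that the other arm stays complete, and that the protocol's GMTs, SDs and unadjusted t-test apply rather than the Tukey-Kramer analysis. The loss that could actually be recovered is smaller, since subjects stopped before Day 28 would not have had the full assigned regimen. The conflict between the sections does not depend on these figures.

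The pregnancy inconsistency is separate and real. Both should be settled before the clause is ever needed.

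**What to change.** By amendment:

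1. Reconcile the treatment-group and entire-study rules in 11.3 with 6.1, 8.2.9, 11.2, 13.2 and 14.5. The text should separate stopping study injections from ending study participation, as the individual rules in 11.3 already do, and state whether the scheduled safety and immunogenicity visits to Day 224 still apply to these subjects.
2. Define which subjects a dropped dose level or discontinued group concerns, including control-vaccine recipients, those who have so far had only placebo, and M1/M2.
3. Reconcile 7.4, 11.3 d and 14.7, so that a pregnant subject has one stated follow-up status.

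The point at which vaccination stops is not part of this change. The cost is amendment wording, since the visits and samples are already in the schedule. If the visits are kept, the small downside is that subjects no longer receiving injections attend visits that they would otherwise skip.

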**12 LABELING, STORAGE AND TRANSPORT OF SAMPLES**

A detailed Lab Manual will be available with information about labeling and transport of the vials.

**12.1 Labeling of samples**

Each sample tube will be clearly and unequivocally identifiable by a label resistant to the storage temperature, which contains the following information:

Study code, site number, subject number, visit code and collection date.

## 12.2 Samples storage

Aliquots of samples will be stored at -95°C to -65°C in a temperature monitored freezer. The temperature will be controlled either by a connected central monitoring system or a Min/Max thermometer, which will be controlled and documented each working day.

## 12.3 Transport of samples

Study samples packed in sufficient solid CO2 will be shipped by an authorized courier from the study site to the sponsor or to an analytical laboratory outside the hospital, if necessary.

## 13 STATISTICAL METHODS AND SAMPLE SIZE

The data will be analyzed by Assign Data Management and Biostatistics GmbH. A Statistical Analysis Plan (SAP) will be provided before database snapshot/closure describing in more detail how the study results will be evaluated.

A preliminary analysis including safety and immunogenicity data will be performed after all subjects completed Visit 3 (day 56). The goal of this analysis is to provide highly valuable data of the novel Chikungunya vaccine for further development. Results from this analysis will have no impact on the study design and treatment of the subjects in this study. A final analysis will be conducted once the last subject has completed the study.

### 13.1 Immunogenicity Analysis

The primary immunogenicity analysis will compare the anti-chikungunya PRNT50 antibody geometric mean titer (GMT) 28 days after one or two immunizations in the Per Protocol (PP) analysis population between the treatment groups. GMTs and GMT ratios will be estimated by applying an analysis of variance including the factor vaccination group. This will be done using log-10 transformed data and taking the anti-log of the resulting point estimates for the least squares means, least squares means differences and the corresponding 2-sided 95% CIs. P-values will also be provided to compare GMTs for the MV-CHIK groups (pairwise comparisons adjusted for multiple comparisons according to Tukey-Kramer; groups A vs. B, C vs. D, M1 vs. M2), e.g. 28 days after the 2nd MV-CHIK dose, etc. Likewise, SCRs will also be compared between groups. Seroconversion will be defined as anti-Chikungunya PRNT50 titers  $\geq 10$ .

Measles ELISA titers will be analyzed as described above. In addition, the effect of pre-existing anti-measles immunity will be assessed: The CHIKV PRNT50 titers 28 days after first vaccination, between the four baseline measles titer groups, defined by baseline percentiles

(25%, 25-50%, 50-75%, 75-100%), will be compared. No stratification by dose groups is intended.

### 13.2 Safety Analysis

Solicited AEs (reactogenicity): Solicited local and solicited systemic AEs will be summarized for the 7 day period, by AE grade (mild, moderate, severe), by group and by dose. Solicited AEs will not be coded into MedDRA or assessed for relatedness. The number and percentage of subjects with AEs will be presented. Subjects who reported data for a solicited event at any time point during the time period summarized would be included in the denominator for that event. Thus, denominators for each solicited event will not include subjects who were missing all data for that event, during the time period summarized. P-values for AE rates for MV-CHIK vs. Priorix® (or equal control-vaccine), for the same schedule, will be provided in summary tables (pairwise comparisons).

Unsolicited AEs: Separately, the number and percentage of subjects with unsolicited treatment emergent adverse events (TEAEs), medically-attended AEs (MAEs) and serious adverse events (SAEs) will be presented for each treatment group overall and by system organ class/preferred term, and by AE grade, and relatedness. All SAEs and MAEs are also included in TEAE tables. Arthritis AEs, AEs of special interest (AESI), will be included in the TEAE tables. For unsolicited AEs, all subjects entered into the study who receive at least one vaccination will be included in the safety analysis based on the product received (“as treated”), for the time period summarized. P-values for AE rates for MV-CHIK vs. Priorix®, for the same schedule, will be provided in summary tables (pairwise comparisons).

Unsolicited AEs and concomitant diseases will be coded using the MedDRA coding dictionary; concomitant medications will be coded using the WHO Drug Dictionary.

Solicited and unsolicited AEs (local and systemic), MAE, SAE and AESI (arthralgia) will be recorded up to Visit 6 (day 224).

Safety analyses will be performed by means of descriptive measures. Laboratory values will be assigned a grade. Changes in laboratory values and grades as well as vital signs from study entry to end of treatment/follow up will be analyzed descriptively.

